4.2.5.3 Adverse events of special interest (AESI)

Preferred terms used to identify AESI will be listed before DBL and documented in the Trial Master File. Grouped summary tables of certain MedDRA preferred terms will be produced and may also show the individual preferred terms which constitute each AESI grouping. Groupings will be based on preferred terms provided by the medical team prior to DBL, and a listing of the preferred terms in each grouping will be provided.

Summaries of the above-mentioned grouped AE categories (the number and percent of patients per treatment group) by system organ class and preferred term will be tabulated for:

- All AESIs
- All AESIs possibly related to study medication (savolitinib only, osimertinib/placebo only, or both savolitinib and osimertinib/placebo only)

- All AESIs by maximum reported CTCAE grade.

4.2.5.4 Vital signs

Summaries of vital signs data will include all data obtained up until 28 days after the last dose of study treatment. Absolute values and change from baseline for diastolic and systolic BP, heart rate, body temperature, height and weight will be summarised at each visit by treatment. The mean, standard deviation, median, minimum value, maximum value, and lower and upper quartiles at each time point will be presented.

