2 ANALYSIS SETS

2.1 Definition of Analysis Sets

Patients will be assigned to the following analysis sets prior to any analyses being performed.

Full Analysis Set (FAS)

The FAS will include all randomised patients with treatment groups assigned in accordance with the randomisation, regardless of the treatment actually received. Patients who were randomised but did not subsequently receive treatment are included in the FAS. The analysis of data using the FAS therefore follows the principles of intention to treat.

The FAS will be the primary population for reporting efficacy data and to summarise baseline characteristics.

Safety analysis set (SAF)

The Safety analysis set will consist of all randomised patients who received any amount of study treatment. Safety data will not be formally analysed but summarised using the safety analysis set according to the treatment received. If a patient receives any amount of an experimental therapy, they will be summarised in the treatment group corresponding to the first experimental treatment they received.

Cross-over analysis set

The Cross-over analysis set will consist of all patients who were randomised to savolitinib in combination with placebo and received at least one dose of savolitinib plus osimertinib in the cross-over period of the study.

It will be used as the population for reporting the efficacy and safety data for patients who crossed over to treatment with savolitinib plus osimertinib following objective progression on savolitinib plus placebo.

PK analysis set

All patients who receive at least one dose of savolitinib or osimertinib as per the protocol, for whom there are at least one reportable PK concentration without any protocol deviation impacting PK, will be included in the PK analysis set. If a patient receives any amount of an experimental therapy, they will be summarised in the treatment group corresponding to the first experimental treatment they received.

Monotherapy analysis set

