4.2.5 Safety

4.2.5.1 General considerations for safety assessments

Time windows will be defined for any presentations that summarise values by visit. The following conventions will apply:

- The time windows will be exhaustive so that data recorded at any time point has the potential to be summarised. Inclusion within the time window will be based on the actual date and not the intended date of the visit.
- All unscheduled visit data have the potential to be included in the summaries.
- The window for the visits following baseline will be constructed in such a way that the upper limit of the interval falls halfway between the two visits (the lower limit of the first post-baseline visit will be Day 2). If an even number of days exists between two consecutive visits, then the upper limit will be taken as the midpoint value minus 1 day. For example, the visit windows for vital signs data are:
 - Day 8, visit window 2 – 11
 - Day 15, visit window 12 – 18
 - Day 22, visit window 19 – 25
 - Day 29, visit window 26 – 43
 - Day 57, visit window 44 – 71
 - Day 85, visit window 72 – 99
 - Day 113, visit window 100 – 127.
- For summaries showing the maximum or minimum values, the maximum/minimum value recorded on treatment will be used (regardless of where it falls in an interval).
- Listings should display all values contributing to a time point for a patient.
- For visit based summaries, if there is more than one value per patient within a time window then the closest value to the scheduled visit date will be summarised, or the earlier, in the event the values are equidistant from the nominal visit date. The listings will highlight the value for the patient that contributed to the summary table, wherever feasible. Note: in summaries of extreme values all post-baseline values

collected are used including those collected at unscheduled visits regardless of whether or not the value is closest to the scheduled visit date.

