- Baseline for safety assessments will generally be the last value obtained prior to the first dose of study medication). Alternatively, if two visits are equally eligible to assess patient status at baseline (e.g., screening and baseline assessments both on the same date prior to first dose with no washout or other intervention in the screening period), the average can be taken as a baseline value. For non-numeric laboratory tests (i.e. some of the urinalysis parameters) where taking an average is not possible then the best value would be taken as baseline as this is the most conservative. In the scenario where there are two assessments on day 1, one with time recorded and the other without time recorded, the one with time recorded would be selected as baseline. Where safety data are summarised over time, study day will be calculated in relation to date of first treatment.
- Per Section 9.4.3 of the CSP, adverse events occurring in the savolitinib in combination with placebo group will be split into two presentations based on whether they occurred before or after cross-over.

Missing safety data will generally not be imputed. However, safety assessment values of the form of “< x” (i.e. below the lower limit of quantification) or > x (i.e. above the upper limit of quantification) will be imputed as “x” in the calculation of summary statistics but displayed as “< x” or “> x” in the listings. Additionally, adverse events that have missing causality (after data querying) will be assumed to be related to study drug.

Furthermore:

- For missing diagnostic dates, if day and/or month are missing, use 01 and/or Jan. If year is missing, put the complete date to missing.
- For missing AE start dates, the following will be applied:
 - a. Missing day: impute the 1st of the month unless month is the same as month of the first dose of study drug then impute first dose date
 - b. Missing day and month: impute 1st January unless year is the same as first dose date then impute first dose date
 - c. Completely missing: impute first dose date unless the end date suggests it could have started prior to this in which case impute the 1st January of the same year as the end date

When imputing a start date ensure that the new imputed date is sensible e.g. is prior to the end date of the AE.

- For missing AE end dates, the following will be applied:

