4.2.5.5 Laboratory summaries

For clinical chemistry and haematology, numerical summaries by treatment group of absolute values and change from baseline will be presented which include the mean, standard deviation, median, minimum value, maximum value, and lower and upper quartiles at each visit in which laboratory values are taken. Shift tables will be produced for CTCAE grade changes, and for baseline to minimum/ maximum values on treatment, in haematology and clinical chemistry parameters, and for baseline to maximum value on treatment for urinalysis parameters. Plots for laboratory parameters of baseline versus minimum/ maximum post-baseline values will be presented.

The liver function tests will be summarised for each patient with potential Hy's Law, who has ALT or AST > 3x ULN and total bilirubin > 2x ULN at any time during the study by time point, and with elevation in transaminases preceding or coinciding with (on the same day as) the elevation in BILI.

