4.2.5.6 Electrocardiograms (ECGs)

QT interval corrected for heart rate using Fridericia's correction (QTcF) evaluations will be done based on triplicate 12-lead electrocardiograms (ECGs) as indicated in the schedule of activities (SoA) of the CSP. The following ECG variables will be collected: PR interval, QRS duration, QT interval, RR interval, and overall ECG evaluation.

The overall evaluation of an ECG will be either "normal" or "abnormal" with abnormalities categorised as either "clinically significant" or "not clinically significant".

Summaries of ECG data will include all data obtained up to and including 28 days after the date of the last dose of study treatment. The ECG assessment at baseline versus end of treatment will be presented by treatment group. Absolute values and change from baseline will be summarised at each visit by treatment group.

For QTc, there are 3 recordings at each visit and therefore for the analysis the average of the non-missing values will be taken as the result at that visit. The QTcF will be calculated in the eCRF as follows (where QT and RR are in seconds):

$$QTcF = \frac{QT}{\sqrt[3]{RR}}$$

The number and percentage of patients with a maximum post-baseline QTcF result exceeding ICH boundaries will be presented by treatment group, both as absolute values and as increases from baseline.

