4.2.5.7 Multi-gated Acquisition (MUGA)/Echocardiogram (ECHO)

An ECHO or MUGA scan to assess left ventricle ejection fraction will be conducted during the main study screening period, Q12W (\pm 2 weeks) relative to randomisation, and at the end of treatment as indicated in the SoAs of the CSP. Absolute values at baseline and end of treatment visit and change from baseline to end of treatment visit for LVEF results will be summarised.

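### Only adverse events are split at cross-over: the SAP sets no cross-over cut-off for exposure, vital signs, ECG or laboratory data in the savolitinib plus placebo arm

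*SAP*

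**What the plan says.** - **Grouping.** Section 2.1 assigns safety-set patients by first treatment: "they will be summarised in the treatment group corresponding to the first experimental treatment they received". A patient who starts on savolitinib plus placebo and later crosses over therefore stays in that column.
- **Adverse events.** Section 4.2.5.1, citing CSP section 9.4.3, says that adverse events in the savolitinib plus placebo group "will be split into two presentations based on whether they occurred before or after cross-over". Section 4.2.10 adds a start rule for the cross-over period, again for AE tables only.
- **Vital signs (4.2.5.4).** "Summaries of vital signs data will include all data obtained up until 28 days after the last dose of study treatment".
- **ECG (4.2.5.6).** Summaries "will include all data obtained up to and including 28 days after the date of the last dose of study treatment".
- **Extreme values (4.2.5.1).** "the maximum/minimum value recorded on treatment will be used (regardless of where it falls in an interval"; a later note in that section brings in every post-baseline value, unscheduled ones included.
- **Laboratory (4.2.5.5).** Shift tables run from "baseline to minimum/ maximum values on treatment".
- **Exposure (3.3.1, 3.3.2, 4.2.5.8).** Total exposure ends at the earliest of last non-zero dose, death and DCO. RDI runs to the last day of dosing. Cycles and the 6- and 12-month exposure counts name no period.
- **LVEF (4.2.5.7).** "change from baseline to end of treatment visit for LVEF results will be summarised".
- **Cross-over set.** Sections 2.1, 4.1 and 4.2.10 provide for safety summaries to be repeated on the cross-over analysis set, where the data are sufficient.

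**The concern.** The safety objective is described by arm: savolitinib with placebo beside savolitinib with osimertinib. If values and dosing recorded after cross-over stay in the placebo column, that column describes a mixture of the two regimens, and any real difference between arms looks smaller. There is also a mismatch inside the report. Adverse event counts for the arm stop at cross-over while exposure carries on, so a reader who relates one to the other understates the monotherapy event rate.

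Cross-over need not be rare. It is allowed after investigator-assessed progression and, under CSP v3.0, is offered to the remaining monotherapy patients after unblinding, subject to sponsor approval (section 1.2).

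**Working it through.** The plan gives no figure to reproduce, so the check has two parts: a reading of each rule for a cross-over stop, and the exposure formula applied to an assumed patient.

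**Rule by rule**

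| Data | End of window in the SAP | Stop or split at cross-over? |
|---|---|---|
| Adverse events (4.2.5.1, 4.2.5.2, 4.2.10) | Safety follow-up after last dose | Yes, explicit split |
| Total and actual exposure (3.3.1) | Last non-zero dose, death or DCO | No |
| RDI, cycles (3.3.1, 3.3.2, 4.2.5.8) | Last day of dosing; none stated for cycles | No |
| Vital signs (4.2.5.4) | 28 days past last dose | No |
| ECG, maximum QTcF (4.2.5.6) | 28 days past last dose; any post-baseline maximum | No |
| Laboratory extremes (4.2.5.1, 4.2.5.5) | On treatment, or any post-baseline value | No |
| Potential Hy's Law (4.2.5.5) | Any time in the study | No, but shown per patient by time point |
| LVEF (4.2.5.7) | End-of-treatment visit | Unclear which period |

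For by-visit tables, section 4.2.5.1 makes the windows exhaustive and counts study day from first treatment. A value after cross-over therefore falls into a later visit of the savolitinib plus placebo column. Visits before cross-over are not affected.

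**Exposure formula.** Total exposure = end date − first dose date + 1. Assumed dates: first dose Day 1, last savolitinib plus placebo dose Day 84, first combination dose Day 98.

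- Stopped at the last dose before cross-over: 84 − 1 + 1 = 84 days.
- Gap: Days 85 to 97 = 13 days.
- *Short combination period*, one 28-day cycle: last dose Day 98 + 28 − 1 = 125. As written, 125 − 1 + 1 = 125 days. Excess 125 − 84 = 41 days (13 + 28). Ratio 125/84 = 1.49.
- *Long combination period*, last dose Day 252: as written, 252 − 1 + 1 = 252 days. Excess 252 − 84 = 168 days (13 + 155). Ratio 252/84 = 3.0. If the gap is recorded as an interruption, actual exposure is 252 − 13 = 239 days against 84.

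In the long case the patient would count under savolitinib plus placebo as treated for at least 6 months, which 84 days would not support.

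**Narrow reading of study treatment.** Suppose the term means randomised treatment only. The vital signs and ECG window for the same patient would then end on Day 84 + 28 = 112, which still covers Days 98 to 112, that is 15 days of combination dosing. Such overlap is likely in general. The progression scan should fall within 28 days of the first cross-over dose (footnote to Table 1), and patients who switch after unblinding may have no gap at all.

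**The case against.** The best reply is that an open window is not a pooling rule. The AE window in section 4.2.5.2 also runs to the end of all study intervention, yet AEs are split. The 28-day limits for vital signs and ECG could likewise be outer bounds on data, with periods assigned elsewhere. The cross-over set gives later data a planned place, and CSP section 9.4.3, which is not at hand, might deal with the other domains.

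Part of this stands. The SAP never says in words that post-cross-over data belong to monotherapy. But AEs escape the open window only because a separate sentence splits them, and no such sentence exists for the other data. Section 3.1 also speaks of stopping study intervention after cross-over, so the term is not confined to the randomised period. Repeating summaries on the cross-over set shows the data again without removing them from the main column, and section 4.2.10 gives no start date or baseline for non-AE data.

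Some stronger readings are not supported:

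- **Every later abnormality is charged to savolitinib alone, and osimertinib toxicity is hidden.** In extreme-value tables a later value counts only if it is the worst, early visits are untouched, and the cross-over tables are planned.
- **LVEF is measured after the combination.** The end-of-treatment visit is not tied to a period, and the SAP points to CSP schedules that are not shown. It is ambiguous, not wrong.
- **Hy's Law cases are misattributed.** They are displayed per patient by time point, so timing relative to cross-over can be recovered.
- **The reported savolitinib duration is false.** Exposure is defined by component, and time on savolitinib after cross-over is real savolitinib exposure. The fault is the arm label and the mismatch with AE counts.

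**Conclusion.** The point holds as a missing cut-off with a definite consequence. As written, the rules for exposure, RDI, cycles, vital signs, ECG and laboratory data let combination-period values enter the savolitinib plus placebo summaries, while AE counts for that arm are cut at cross-over. Support is strongest for exposure (an explicit formula) and for vital signs and ECG (explicit windows). For laboratory shift tables it rests on the on-treatment wording carrying no period limit. LVEF and Hy's Law need clarification only.

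The size cannot be stated. It depends on how many patients cross over and when, which the SAP does not give. The whole arm is a ceiling, since patients may stay on monotherapy. The 1.49- and 3.0-fold exposure ratios illustrate single patients with assumed dates and do not estimate an arm-level effect.

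This should be fixed but is not critical: safety is summarised without formal analysis, and the primary endpoint, ORR, does not use these data.

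**What to change.** In sections 3.3.1, 3.3.2 and 4.2.5:

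1. For patients who cross over, end the main by-arm window for exposure, RDI, dose interruptions, cycles, laboratory, vital signs and ECG data before the first cross-over dose. For all others keep the existing end date.
2. Report later data only in the cross-over tables, and state their start date and baseline for non-AE data.
3. Confirm that those tables will be produced for everyone in the cross-over set, including patients who switch after unblinding without progression. Section 2.1 defines the set to include them but describes its use only for progressors, and section 4.2.10 makes the analyses conditional on sufficient data.
4. State whether the LVEF end-of-treatment visit is that of the randomised or the cross-over period.
5. Label potential Hy's Law records as before or after cross-over.

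The cost is SAP wording and wider use of the cross-over date already needed for the AE split. The drawback is shorter follow-up in the monotherapy columns.

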4.2.5.5 Laboratory summaries

For clinical chemistry and haematology, numerical summaries by treatment group of absolute values and change from baseline will be presented which include the mean, standard deviation, median, minimum value, maximum value, and lower and upper quartiles at each visit in which laboratory values are taken. Shift tables will be produced for CTCAE grade changes, and for baseline to minimum/ maximum values on treatment, in haematology and clinical chemistry parameters, and for baseline to maximum value on treatment for urinalysis parameters. Plots for laboratory parameters of baseline versus minimum/ maximum post-baseline values will be presented.

The liver function tests will be summarised for each patient with potential Hy's Law, who has ALT or AST > 3x ULN and total bilirubin > 2x ULN at any time during the study by time point, and with elevation in transaminases preceding or coinciding with (on the same day as) the elevation in BILI.

4.2.5.6 Electrocardiograms (ECGs)

QT interval corrected for heart rate using Fridericia's correction (QTcF) evaluations will be done based on triplicate 12-lead electrocardiograms (ECGs) as indicated in the schedule of activities (SoA) of the CSP. The following ECG variables will be collected: PR interval, QRS duration, QT interval, RR interval, and overall ECG evaluation.

The overall evaluation of an ECG will be either "normal" or "abnormal" with abnormalities categorised as either "clinically significant" or "not clinically significant".

Summaries of ECG data will include all data obtained up to and including 28 days after the date of the last dose of study treatment. The ECG assessment at baseline versus end of treatment will be presented by treatment group. Absolute values and change from baseline will be summarised at each visit by treatment group.

For QTc, there are 3 recordings at each visit and therefore for the analysis the average of the non-missing values will be taken as the result at that visit. The QTcF will be calculated in the eCRF as follows (where QT and RR are in seconds):

$$QTcF = \frac{QT}{\sqrt[3]{RR}}$$

The number and percentage of patients with a maximum post-baseline QTcF result exceeding ICH boundaries will be presented by treatment group, both as absolute values and as increases from baseline.

4.2.5.7 Multi-gated Acquisition (MUGA)/Echocardiogram (ECHO)

An ECHO or MUGA scan to assess left ventricle ejection fraction will be conducted during the main study screening period, Q12W (\pm 2 weeks) relative to randomisation, and at the end of treatment as indicated in the SoAs of the CSP. Absolute values at baseline and end of treatment visit and change from baseline to end of treatment visit for LVEF results will be summarised.

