
To evaluate the efficacy of savolitinib plus osimertinib in patients who cross-over after progression on savolitinib plus placebo. ^a
	
 • Objective response rate is defined as the proportion of patients with measurable disease who have a CR or PR as determined by the investigator at the local site per RECIST 1.1. • Progression-free survival is defined as time from the first dose in the cross-over period until progression per RECIST 1.1 as assessed by the investigator or death due to any cause. • Duration of response is defined as the time from the date of first documented response during the cross-over period until date of documented progression per RECIST 1.1 as assessed by the investigator or death in the absence of disease progression. • Tumour size assessment is defined as the percentage change from baseline in TLs at 12 weeks per RECIST 1.1 as assessed by the investigator.

To evaluate the PK of savolitinib and osimertinib.
	
Plasma concentrations of savolitinib, osimertinib, and their metabolites.

To determine the prevalence of ctDNA clearance after savolitinib plus osimertinib or savolitinib plus placebo treatment in this patient population.
	
Total clearance in EGFR mutations at 6-weeks after therapy initiation (percentage and absolute change from baseline in EGFR mutation allele frequencies).

Safety objective:
	
Safety endpoints/variables:

To evaluate the safety and tolerability of savolitinib plus osimertinib or savolitinib plus placebo.
	
Safety and tolerability will be evaluated in terms of AEs, SAEs and discontinuation rate due to AEs. Clinical chemistry/haematology including LFTs, ECHOs, ECGs and vital signs including blood pressure and heart rate.

Tertiary/exploratory objectives:
	
Tertiary/exploratory endpoints/variables:

^a Baseline for ORR, PFS, DoR and tumour size assessments of patients who cross-over to savolitinib plus osimertinib from savolitinib plus placebo will be the progression scan on savolitinib plus placebo acquired within 28 days of the start of treatment in the cross-over period.

CCI

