4.2.4 Data cut-offs

The data cut-off for futility analysis was planned to take place after 20 patients overall (10 per arm) have had the opportunity to be treated for 2 RECIST post-baseline scans (12 weeks). In order to ensure that 10 patients in the savolitinib plus placebo group have been randomised for inclusion into the futility analysis set, the IWRS was to be used to determine when 22 patients have been randomised into the study.

The data cut-off for primary analysis was planned to take place 6 months after last subject in (LSI). The data cut-off for final analysis was planned to take place at the earlier of 18 months after LSI or when 70% of patients have progressed or died.

Under CSP v3.0, an initial DCO will occur to allow an early review of data by AstraZeneca. A final DCO will occur 9 months after the last patient has been randomised, after which the final analysis will be performed. CCI These changes are a result of the decision by AstraZeneca to terminate study recruitment early.

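### LVEF is scanned every 12 weeks but summarised only at baseline and end of treatment, so recovered on-treatment falls and the post-baseline values of patients still on treatment at the cut-off enter no LVEF summary

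*SAP*

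**What the plan says.** Table 1 (Section 1.1) names echocardiograms among the safety variables: "Clinical chemistry/haematology including LFTs, ECHOs, ECGs and vital signs including blood pressure and heart rate".

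Section 4.2.5.7 sets the collection schedule: "An ECHO or MUGA scan to assess left ventricle ejection fraction will be conducted during the main study screening period, Q12W", with a window of two weeks either side relative to randomisation, and again at end of treatment. The analysis is one sentence: "Absolute values at baseline and end of treatment visit and change from baseline to end of treatment visit for LVEF results will be summarised".

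The neighbouring sections go further. For ECGs, Section 4.2.5.6 compares baseline with end of treatment, and adds "Absolute values and change from baseline will be summarised at each visit by treatment group" and "The number and percentage of patients with a maximum post-baseline QTcF result exceeding ICH boundaries will be presented by treatment group". For laboratory data, Section 4.2.5.5 gives summaries at each visit and shift tables "for baseline to minimum/ maximum values on treatment, in haematology and clinical chemistry parameters". Vital signs (Section 4.2.5.4) are summarised at each visit.

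On timing, Section 4.2.4 states: "A final DCO will occur 9 months after the last patient has been randomised, after which the final analysis will be performed".

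**The concern.** The plan collects repeated LVEF measurements and then tabulates only the two ends of the series. There are two consequences.

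- A fall seen at week 12 or week 24 that has recovered by the end-of-treatment visit appears in no LVEF table.
- A patient still on treatment at the final cut-off has no end-of-treatment visit, and so has neither a post-baseline LVEF value nor a change from baseline in the summary. Among patients randomised at a similar time, these are the ones with the longest exposure.

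At stake is whether the study report can describe what happened to measured LVEF during treatment, for a variable that the SAP itself lists under its safety objective.

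**Working it through.** **1. Does another section fill the gap?** The general convention in Section 4.2.5.1 reads "For summaries showing the maximum or minimum values, the maximum/minimum value recorded on treatment will be used". It says how an extreme is chosen where such a summary is planned. No LVEF extreme is planned, so it creates no table. Table 2 has no LVEF row. The general statement in Section 4.1 that descriptive statistics will be used does not override a section that names its own two time points. The SAP does not define the end-of-treatment visit as the last available on-treatment value.

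**2. Planned depth, side by side.**

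| Data | Baseline vs end of treatment | Each visit | On-treatment or post-baseline extreme |
|---|---|---|---|
| Laboratory (4.2.5.5) | – | yes | yes (shift tables) |
| ECG (4.2.5.6) | yes | yes | yes (maximum QTcF) |
| Vital signs (4.2.5.4) | – | yes | not specified |
| LVEF (4.2.5.7) | yes | no | no |

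**3. Scans left unused.** The last patient randomised is followed for 9 months to the final cut-off:

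9 × 30.44 / 7 = 39.1 weeks.

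Scheduled post-baseline scans by then: floor(39.1 / 12) = 3, at weeks 12, 24 and 36. The third falls by week 38 even if it is two weeks late. A patient randomised earlier and treated through to the cut-off has at least as many. The planned summary uses at most one post-baseline scan per patient (end of treatment), and none for a patient still on treatment.

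**4. Are such patients foreseen?** Yes. Section 4.2.3.1 counts patients who have not progressed and remain on treatment at the analysis. Section 1.2 lets patients stay on savolitinib plus placebo after unblinding. Section 3.3.1 truncates exposure at the cut-off.

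**5. How many?** The SAP does not say. As an illustration only, assume exponential time on treatment with median m months, so λ = ln 2 / m, and uniform accrual over A months. Follow-up is then uniform on 9 to 9 + A months, and

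P(still on treatment) = [exp(−9λ) − exp(−(9 + A)λ)] / (Aλ).

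- m = 3, A = 12: λ = 0.2310; (0.1250 − 0.0078) / 2.773 = 0.04
- m = 4, A = 12: λ = 0.1733; (0.2102 − 0.0263) / 2.079 = 0.09
- m = 6, A = 12: λ = 0.1155; (0.3536 − 0.0884) / 1.386 = 0.19
- m = 10, A = 12: λ = 0.0693; (0.5359 − 0.2333) / 0.832 = 0.36
- m = 10, A = 6: λ = 0.0693; (0.5359 − 0.3536) / 0.416 = 0.44

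Only the 9 months comes from the SAP. The medians, the accrual periods and the exponential form are assumptions.

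**The case against.** Section 4.2.5.7 is clear, can be programmed as written and contradicts nothing. Recruitment stopped short of the planned 56 or so patients, Section 4.2.1 says that no inferential analyses are planned, and no decision rule depends on LVEF. Tables by 12-weekly visit would hold few patients per arm. That the laboratory and ECG sections go deeper shows uneven depth, not an error. All of this is fair, and it makes this an inexpensive improvement to a descriptive table. It does not explain why scans that are collected on schedule enter no summary.

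Three stronger readings are tempting, and the SAP does not support them.

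- *That patients still on treatment are lost altogether, or that a serious fall could not be seen at all.* Those patients contribute a baseline value, and their scans are still collected. A fall reported as an adverse event would appear in the Section 4.2.5.2 tables, including those by maximum CTCAE grade and those for events leading to interruption, reduction or discontinuation. That route depends on investigator reporting, so it does not replace a summary of measured LVEF.
- *That cardiac safety will look better than it was.* Omitting recovered falls would flatter the result. But an end-of-treatment table contains only patients who stopped, including any who stopped for cardiac reasons, and leaves out those who tolerated treatment and continued. The two effects pull in opposite directions.
- *That cross-over safety is unaddressed.* Table 2 and Section 4.2.10 already assign safety data to the cross-over analysis set, where sufficient data allow. What remains open is narrower. The safety analysis set groups patients by first treatment received, and the explicit split before and after cross-over in Section 4.2.5.1 concerns adverse events. Section 4.2.5.7 does not say which LVEF values of a crossed-over patient belong in the savolitinib plus placebo column.

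**Conclusion.** The point stands as a gap in the LVEF summary. Followed as written, the plan leaves out on-treatment falls that recover before the last visit, and every post-baseline LVEF value of patients still on treatment at the final cut-off. For a patient treated through to that cut-off, this means at least three scheduled scans, provided the 12-weekly schedule is kept. The summary may therefore misrepresent the on-treatment cardiac effect, in a direction that cannot be determined.

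The number of patients affected cannot be computed from the SAP. The illustrative range, from roughly 4% with a median of 3 months on treatment to 44% with a median of 10 months, shows how strongly any percentage depends on that assumption. No single figure in it should be taken as the size of the problem. The conclusion rests on the text of Section 4.2.5.7 and on the absence of any other LVEF summary, not on the percentage.

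**What to change.** In Section 4.2.5.7, in line with the laboratory and ECG sections, add by treatment arm:

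1. LVEF and change from baseline at each 12-weekly visit.
2. The lowest on-treatment LVEF and the largest fall from baseline per patient, including unscheduled scans.

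State that patients without an end-of-treatment scan contribute their on-treatment values to these summaries. For the savolitinib plus placebo arm, use only values before cross-over, and report later values in the safety summaries already planned for the cross-over analysis set. The existing baseline and end-of-treatment summary can stay.

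The cost is one or two extra descriptive tables and a little programming, from data already collected, with no effect on study conduct. The downside is small numbers at each visit. The per-patient minimum and largest fall suffer less from this, because each patient with at least one on-treatment scan counts once.
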